**Protocol Title:**

“Randomized, double blind, cross over study comparing effectiveness of traditional opioids versus opioids in admixture with bupivacaine upon self-administration of boluses via a Personal Therapy Manager (PTM) in Intrathecal pump”.

**ABSTRACT**

**2.1 Purpose:**

To determine whether the local anesthetic bupivacaine delivered intrathecally in small doses via PTM self-administered boluses significantly improves the breakthrough pain and functional status of patients with chronic intractable pain who are managed with an intrathecal drug delivery system.

**2.2 Research Design:**

Randomized, double-blind cross over effectiveness study.

**2.3 Methodology /Technical Approach:**

Seventeen patients who are already using SynchroMed II pump containing an admixture of bupivacaine and an opioid and using PTM doses will be randomized into two groups:

Group I: Will have the intrathecal pumps refilled with 10 milliliters of a solution containing their usual intrathecal opioid with bupivacaine.

Group II: IT pump will be filled with 10 ml of intrathecal opioid without bupivacaine.

Both patients and the evaluating physician will be blinded.

In order to accomplish this, only the central compounding (investigational) pharmacy at University Hospitals Case Medical Center would make two solutions labeled: A or B respectively. Study subjects will be randomized and randomization order will be held at the pharmacy that will supply the medication. Patients will be kept on each solution for one week. Data will be collected daily.

**3. OBJECTIVES AND RATIONALE**

The objective of this project is to conduct a randomized, double-blind, effectiveness study to determine whether intrathecal delivery of bupivacaine via self-administered boluses significantly improves breakthrough pain and functional status in patients with chronic, non-cancer pain who are managed with an implanted intrathecal drug delivery system (IDDS). This is important because some practitioners choose only a mono therapy (i.e. opioid) in the intrathecal solution without bupivacaine. This would delay pain relief without the near instant relief bupivacaine has been reported to provide after a PTM bolus.

University Hospitals Case Medical Center

Department of Anesthesiology

Division of Pain Medicine

Study title: *“Effectiveness of Self-Administered Boluses of Intrathecal Bupivacaine in Patients with Chronic Non-Cancer Pain Implanted with IDDS: A Double Blind Randomized Study”*

Principal Investigator: [name] [name]

#### **4. MEDICAL APPLICATION**

Intrathecal drug delivery is an established interventional modality in managing different chronic pain conditions, especially post laminectomy syndrome, also known as failed back surgery syndrome (FBSS). Intrathecal delivery of pharmacological agents reduces systemic side effects and the potential for aberrant medication use.

Previous publications from our center have demonstrated that bupivacaine in combination with intrathecal opioids results in long term relief and reduces opioid dose escalation—an important problem in intrathecal drug delivery. Particularly, the PTM dosing function with bupivacaine has rapid onset of action (given bupivacaine site of action preferentially on nerve rootlets) which significantly improves patient satisfaction.

#### **5. BACKGROUND AND SIGNIFICANCE**

Treatment of chronic pain is a challenging endeavor and intrathecal drug delivery is an important tool in the armamentarium of Pain Medicine specialists.

Continuous intrathecal drug delivery is an interventional modality often applied in refractory chronic pain of cancer or non-cancer etiology. Intrathecal drug delivery systems (IDDS's) involve programmable pumps that constantly deliver the medication into the spinal canal but also may allow the patients to self-administer a dosage of medication that is pre-determined by the clinician in terms of dose and frequency. The use of this latter feature helps control emergent (breakthrough) pain and/or preempts predictable mechanical pain. The patient is provided with a remote control device (called Personal Therapy Manager—PTM) that is easy to use and allows self-administration of boluses.

Standard of care medications used in IDDS include opioids such as morphine or hydromorphone and the local anesthetic bupivacaine. A combination of an opioid with bupivacaine is used in the vast majority of patients implanted at University Hospitals Case Medical Center.

Opioid medications work by binding to opioid receptors in the substantia gelatinosa in the dorsal horn of the spinal cord. Hence, the opioid would have to diffuse 1-2 mm below the surface of the spinal cord in order to reach its target and effect pain relief. Similar to other local anesthetics, bupivacaine works by blocking sodium channels. While these are distributed ubiquitously in the nervous system, it is much more efficient for bupivacaine to bind to sodium channels on nerve rootlets (fila radicularia or small branches that divide off each nerve root before it plugs into the cord). This may explain why many patients

University Hospitals Case Medical Center

Department of Anesthesiology

Division of Pain Medicine

Study title: *“Effectiveness of Self-Administered Boluses of Intrathecal Bupivacaine in Patients with Chronic Non-Cancer Pain Implanted with IDDS: A Double Blind Randomized Study”*

Principal Investigator: [name] [name]

who use a PTM to self-administer boluses report instant pain relief when bupivacaine is present in the intrathecal pump solution.

The effective analgesic PTM dose of bupivacaine is 0.4-1.5 mg and is self-administered with a lock-out interval of 15-120 minutes as needed for pain control. The dose is titrated for analgesic effectiveness without causing motor impairment.

## **6. PLAN**

**6.1 New Investigational Drugs/ Investigational Devices Exemption Status:** N/A

### **6.2 Selection of Subjects**

#### **6.2.1 Type of the Subject Population**

Patients with intractable chronic pain being managed with an intrathecal drug delivery system programmed with a continuous infusion as well as a self-administered bolus (PTM) for breakthrough pain who have an opioid as well as bupivacaine in the intrathecal solution and have been stable on their current settings for at least 3 months.

#### **6.2.2 Inclusion and Exclusion Criteria**

##### **a. Inclusion Criteria**

- Age more than 30 years implanted with an intrathecal drug delivery device.
- Intrathecal pump patients on stable dose for the last 3 months.
- Using on average more than 2 and less than 10 PTM doses per day
- Intrathecal medication admixture consisting of bupivacaine and another opioid (fentanyl or hydromorphone or morphine)

##### **b. Exclusion Criteria**

- Using 10 or more PTM bolus doses per day or 2 or less PTM bolus doses per day
- Pending litigation or worker compensation claim
- Any recent (less than 3 month) procedures in spine (surgeries) or catheter adjustments.
- Recent pump dose adjustment within the past 3 months
- Pumps with medications other than bupivacaine opioid combination.

#### **6.2.3 Recruitment**

Subjects will be recruited from among patients seen at the University Hospitals pain clinic at UHCMC by attending physicians. Screening will be done before obtaining consent by an investigator. Screening for stable programmed mode and dose of medication for at least

University Hospitals Case Medical Center  
Department of Anesthesiology  
Division of Pain Medicine  
Study title: *“Effectiveness of Self-Administered Boluses of Intrathecal Bupivacaine in Patients with Chronic Non-Cancer Pain Implanted with IDDS: A Double Blind Randomized Study”*  
Principal Investigator: [name] [name]

three months. Except for parking pass and meal pass, no subject will be compensated for participation.

#### **6.2.4 Consent Process**

The Principal Investigator and/ or associate investigators will present and explain in detail the consent and HIPAA authorization forms to potential participants. If interested, eligible individuals will be given the opportunity to ask and have all questions answered before signing the informed consent document and HIPAA authorization form.

Subjects will be consented by one of the investigators after they are screened by a pain clinic attending for eligibility, before having their intrathecal drug delivery system refilled. In subjects who elect to participate, the consent form will be taken home to be examined and after a detailed explanation is given, will be signed in the clinic during the next visit for the refill. An explanation in lay terms for the reason of the study and the proposed effectiveness bupivacaine has on near immediate relief of breakthrough pain will be used to promote patient understanding.

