Secondary outcome measures will include average NRS pain scores for the day, functional capacity as evaluated by the Oswestry disability index (ODI) scores, number of boluses used, paresthetic sensation post bolus, and Global Perceived Effect.

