
University Hospitals Case Medical Center  
 Department of Anesthesiology  
 Division of Pain Medicine  
 Study title: “*Effectiveness of Self-Administered Boluses of Intrathecal Bupivacaine in Patients with Chronic Non-Cancer Pain Implanted with IDDS: A Double Blind Randomized Study*”  
 Principal Investigator: [name] [name]

patient will be able to self-administer PTM doses. When doing so, the patients will be receiving either opioid + bupivacaine (exactly similar to baseline) or opioid alone (similar

to baseline but without bupivacaine). Hence, patients will continue to have access to PRN (as necessary) analgesia with self-administered PTM doses. As patients will be kept on solution A or solution B for a maximum of one week each, the maximal duration without bupivacaine in the intrathecal bolus would be one week.

The patients will be provided with a paper diary that will be attached by Velcro to the PTM remote device which will act as a reminder for patients to record pain scores prior to the PTM bolus. The patients will also record the lowest pain scores within the first 30 minutes after a PTM bolus. Only the first 3 successful PTM boluses per day will be recorded and tracked by the study. The patients will also record the average NRS score and GPE score daily. Reminders to complete the diary will also be provided to patients via phone, email or text message.

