**6.4.1 The primary endpoints (i.e., primary outcome variables) and the secondary endpoints, if any.**

University Hospitals Case Medical Center

Department of Anesthesiology

Division of Pain Medicine

Study title: “*Effectiveness of Self-Administered Boluses of Intrathecal Bupivacaine in Patients with Chronic Non-Cancer Pain Implanted with IDDS: A Double Blind Randomized Study*”

Principal Investigator: [name] [name]

The primary outcome variable will be the average change in the NRS for back pain scores between NRS scores before PTM bolus and NRS scores within 30 minutes after PTM bolus. Secondary outcome variables will be Oswestry disability score, satisfaction (categorical “positive” or negative”), the Global Perceived Effect score and side effects (medications). These variables will be recorded at baseline and during each follow-up visit. Global Perceived Effect and Oswestry questionnaires (as well as adverse effects) will be collected at baseline and at the end of each one-week study period.

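### The planned consent explanation gives patients the expected direction and timing of the self-rated 30-minute primary endpoint; any expectation bias would favour bupivacaine, and neutral wording would reduce it at almost no cost

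*Combined protocol and SAP*

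**What the plan says.** On consent, Section 6.2.4 states that, alongside the reason for the study, "the proposed effectiveness bupivacaine has on near immediate relief of breakthrough pain will be used to promote patient understanding".

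On blinding, Section 2.3 states: "Both patients and the evaluating physician will be blinded". Section 6.3.2 supports this in two ways. Only the investigational pharmacy knows the contents of each solution. The pump is also programmed with a bupivacaine label of 29 mg/ml at the first refill and 30 mg/ml at the second, whichever solution is given.

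On the endpoint, Section 6.4.1 begins: "The primary outcome variable will be the average change in the NRS for back pain scores between NRS scores before PTM bolus", and takes the second score within 30 minutes after the bolus. Section 6.3.2 says who supplies it: "The patients will also record the lowest pain scores within the first 30 minutes after a PTM bolus". The record is a paper diary.

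On what patients already know, the inclusion criteria require "Intrathecal medication admixture consisting of bupivacaine and another opioid (fentanyl or hydromorphone or morphine", a dose stable for 3 months, and on average more than 2 and fewer than 10 boluses a day. Section 5 reports that many patients "who use a PTM to self-administer boluses report instant pain relief when bupivacaine is present in the intrathecal pump solution". The secondary outcomes in Section 6.3.1 include "number of boluses used, paresthetic sensation post bolus, and Global Perceived Effect".

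**The concern.** A self-rated pain score is open to expectation. Two conditions make expectation a bias rather than noise: the patient has an idea of which treatment is being given, and the patient has an idea of what that treatment should do. The consent explanation supplies the second, in the same terms as the primary endpoint: relief after a bolus, and soon. Prior daily use of bupivacaine boluses makes the first plausible, because one study week repeats the patient's baseline mixture and the other is that mixture without bupivacaine.

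If some patients recognise the solution and score towards what they were told, the shift follows the solution and not the period or the sequence. Neither randomisation of order nor the within-patient comparison would then remove it, and the primary analysis could not separate it from a drug effect.

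**Working it through.** **Step 1. Does the explanation match the endpoint?**
- Direction: Section 6.2.4 names bupivacaine as the agent proposed to give relief. Section 6.4.1 compares relief with and without it.
- Timing: Section 6.2.4 refers to relief that is nearly immediate. The endpoint window is 30 minutes.
- Rater: the patient, who picks the lowest score in that window.

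All three coincide.

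**Step 2. Do the blinding measures reach this?** Pharmacy coding and the 29/30 mg/ml labels conceal the allocation from staff and patients. They do not alter what a patient feels after a bolus or what a patient was told to expect. The documents contain no treatment-guess question, no check of blinding and no sensitivity analysis for unblinding.

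**Step 3. Is recognition plausible?** All participants know the bupivacaine mixture from daily use. Section 5 says many such patients report instant relief with it. Paresthesia after a bolus is listed as an outcome, so it is thought possible. Recognition is therefore a reasonable inference, but the documents do not state that it happens.

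**Step 4. What would a given shift do?** Inputs from Section 6.4.4: 14 patients, within-patient SD 2, difference 2, power 0.80, two-sided level 0.10. The parameter list there gives 0.05 adjusted for sidedness, which agrees with two-sided 0.10 if it means 0.05 per tail; both two-sided levels are shown below.

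For a two-period crossover t-test, SE = SD × √(2/N) = 2 × √(2/14) = 0.756, with N − 2 = 12 degrees of freedom.

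The plan's own figure comes first. The noncentrality is 2/0.756 = 2.65, and the noncentral t gives power 0.802 at two-sided 0.10. Fourteen is the smallest N that reaches 0.80, so the plan's figure is reproduced.

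Now set the true difference to 0 and let *b* be an assumed average shift in favour of bupivacaine, with noncentrality *b*/0.756. The documents give no value for *b*, so a range is shown. Entries are the probability of a significant result.

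| *b* (NRS points) | N = 14, level 0.10 | N = 14, level 0.05 | N = 17, level 0.10 | N = 17, level 0.05 |
|---|---|---|---|---|
| 0 | 0.10 | 0.05 | 0.10 | 0.05 |
| 0.25 | 0.12 | 0.06 | 0.12 | 0.06 |
| 0.5 | 0.17 | 0.09 | 0.18 | 0.11 |
| 1.0 | 0.35 | 0.23 | 0.40 | 0.28 |
| 1.5 | 0.59 | 0.45 | 0.67 | 0.53 |

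The columns for 17 assume that every recruited patient completes. The shift is an average over all patients: if half of them recognise the solution and each of those shifts by 0.5 point, then *b* = 0.5 × 0.5 = 0.25, and the 10% rate becomes 12%.

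**The case against.** The other side has good arguments, and several stand.

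- **Consent has to explain the study.** Bupivacaine is withdrawn for up to a week (Section 6.3.2), and poor pain control is listed as a possible side effect (Section 6.5.1). Patients need to know what they may lose. This stands as a limit on the fix: disclosure must stay, and only the prediction needs to go.
- **The sentence says the effect is proposed, and the consent form was not available for review.** The form may already say that the answer is unknown. This stands as a caveat. Section 6.2.4 still plans for the predicted benefit to be part of the explanation.
- **Patients arrive with expectations.** Months of bupivacaine boluses shape belief more than one sentence can. This stands: neutral wording reduces one source of bias and does not remove expectation.
- **Recognition through relief is the effect under test.** This is partly right, and it limits the table. If there is truly no difference in relief, relief cannot reveal the solution, and recognition would have to come through another cue, such as paresthesia or a departure from the familiar mixture.

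A reader might also infer more than the documents support. They do not say that paresthesia is recorded after every bolus: Section 6.3.1 only lists "paresthetic sensation post bolus" as an outcome, the described diary has no entry for it, and no passage says that its rate differs between solutions. Section 5 speaks of many patients, not of all those to be enrolled.

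**Conclusion.** The point holds as a modest and avoidable weakness. The planned explanation primes the direction and timing of a patient-rated primary endpoint, and the existing blinding measures do not address priming. Any bias that resulted would favour bupivacaine.

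It would be tempting to conclude that the blind will fail, or that the consent wording raises the false-positive rate to 17% or 35%. Neither is supported. Unblinding is an inference from familiarity and reported rapid relief. The probabilities describe any bias of the assumed size (no true difference, within-patient SD 2, a shift averaged over all patients) and do not say how much of it the wording would cause. They show only that, in a trial this small, a shift of a quarter to half of the 2-point design difference is enough to matter.

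**What to change.** Replace the sentence in Section 6.2.4 with neutral wording, for example: the study compares pain relief after boluses with and without bupivacaine, and whether one gives better relief is what the study is testing. Keep the full disclosure that one study week is without bupivacaine and that poor pain control is possible. Check that the consent form and any spoken script match.

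Optionally, add one item to the questionnaires already collected at the end of each one-week period (Section 6.4.1), asking which solution the patient thinks was given and why, and report it descriptively by solution. This would not change the primary result. It has two downsides: a correct guess may reflect true efficacy, and asking after week 1 may prompt patients to look for differences in week 2.

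The cost is a change of consent wording and, if wanted, one questionnaire item at visits already planned. Treatment, visits and sample size are unaffected.

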### **6.3 Study Design and Methodology**

#### **6.3.1 Study Design**

This is a randomized, double-blind, effectiveness study looking at self-administered boluses of an opioid with and without bupivacaine via a Personal Therapy Manager (PTM) in patients with an intrathecal drug delivery system to assess the effect of bupivacaine administered by PTM on pain scores and functional status in patients with breakthrough pain. Patients in group I will receive a refill of a 10 mL solution “A” containing their usual intrathecal opioid and including bupivacaine. Patients in group II will receive a refill of a 10 mL solution “B” containing their usual intrathecal opioid without bupivacaine. Both groups will be kept on solution A and on solution B for a maximum of one week each after which they will cross over to the other solution for one week and then exit the study. The patients will then be returned to their baseline programming. Potential changes in programming to benefit patients may be undertaken as necessary—if existent—after unblinding. Primary outcome measures will include 0-10 numerical rating scale (NRS) or Visual Analogue Scale (VAS) both immediately before and within 30 minutes after a PTM bolus. Patients will be provided with a diary to record pain scores just before a PTM bolus and the lowest pain score within half an hour after a PTM bolus. Only 5 recording per day will be available on the diary—thus patients would record pain scores only before and after the first 5 PTM boluses. However, the scores before and after the first 3 successful PTM boluses would be the only ones considered. Successful PTM activations would be determined by review of the patient PTM diary and the internal log from the intrathecal drug delivery system. Each recording on the PTM diary would be time matched to the successful PTM activation code in the internal log. This will obviate any potential mis-administered bolus whereby the patient does not activate the bolus device appropriately.

University Hospitals Case Medical Center

Department of Anesthesiology

Division of Pain Medicine

Study title: *“Effectiveness of Self-Administered Boluses of Intrathecal Bupivacaine in Patients with Chronic Non-Cancer Pain Implanted with IDDS: A Double Blind Randomized Study”*

Principal Investigator: [name] [name]

Secondary outcome measures will include average NRS pain scores for the day, functional capacity as evaluated by the Oswestry disability index (ODI) scores, number of boluses used, paresthetic sensation post bolus, and Global Perceived Effect.

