At each of the first two visits following signing of informed consent Patient should be refilled in the IDD pumps with a 10 mL solution containing either the usual intrathecal medications (solution A or Solution B—coded by pharmacy) including bupivacaine with the opioid (same intrathecal solution) or their usual intrathecal solution with the same opioid concentration but without bupivacaine. Taking away bupivacaine from the intrathecal solution does not result in withdrawal. The investigational pharmacy at UHCMC would be the only party who knows whether the patients are receiving solution A or solution B. No changes will be recorded in pump programming with respect to the opioid. However, upon each of the two first visits after consent, when the patients are refilled with 10 ml of solution A or solution B, the pump will be programmed with the same concentration of the opioid and bupivacaine labeled at 29 mg/ml at the first visit and 30 mg/ml at the second visit. Changing the solution at the first visit to a label of bupivacaine 29 mg/ml will not affect the delivery of the opioid or bupivacaine (if the solution has bupivacaine) as the only (and primary) driver for amount delivered is the opioid which will not change in concentration or dose throughout the study. However, labeling the bupivacaine with 29 mg/ml (a concentration not used and different from previous bupivacaine concentration) will prompt the decision algorithm to request a “bridge bolus”—namely, a calculation of how long it would take for the new solution to get through the dead space in the pump and catheter to get to the catheter tip. Upon changing the solution in the pump, it may take about a day or so for the new medication to enter the intrathecal space because of dead space. The exact duration is dependent on the patient’s initial rate (ml/day) the length of the catheter in the patient; thus would vary from patient to patient. The dead space in the Medtronic SynchroMed II pump is comprised of the internal tubing within the pump (0.199 ml) + external catheter tubing extending from the pump to the Intrathecal space (usually about 0.1 to 0.15 ml). This amount is calculated at pump change and is usually on the order of one day, but varies and the pump programmer will calculate the exact date when the bridge bolus is completely delivered. Importantly, during the bridge bolus, the patients will not be able to self-administer PTM boluses. Many patients may be used to this with solution changes. When the bridge bolus is completely administered, usually after a day or so, the

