A randomization table will be developed by a computer generated random number sequence. This “code” and a copy of all data collection sheets will be kept by our research staff in a locked office and protected by computer passwords as well as the UHCMC compounding pharmacy that will prepare the solutions labeled as described.

**v.** When will you destroy the research source documents, data file, and the master

University Hospitals Case Medical Center  
Department of Anesthesiology  
Division of Pain Medicine  
Study title: “*Effectiveness of Self-Administered Boluses of Intrathecal Bupivacaine in Patients with Chronic Non-Cancer Pain Implanted with IDDS: A Double Blind Randomized Study*”  
Principal Investigator: [name] [name]

code?

The UHCMC research team in the Pain Medicine Clinic will keep the research data for up to six years after the end of the study. Then all the information will be destroyed. The master code will be destroyed as soon as all data collection is completed.

vi. Will research data including Identifiable Protected Health Information be sent outside of UHCMC? No

**6.7.3 HIPAA Authorization Waiver:** N/A- We will obtain signed HIPAA authorization from each patient.

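### The A/B solution labels have one fixed meaning that the protocol itself prints, which conflicts with their being a pharmacy-only code and puts the blind at risk if the letter can be seen

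*Combined protocol and SAP*

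**What the plan says.** **Labelling.** Section 2.3 describes the group with bupivacaine and then the group without it. It then says that the compounding pharmacy "would make two solutions labeled: A or B respectively". Section 6.3.1 gives Group I "a 10 mL solution “A” containing their usual intrathecal opioid and including bupivacaine" and Group II "a 10 mL solution “B” containing their usual intrathecal opioid without bupivacaine", and adds: "Both groups will be kept on solution A and on solution B for a maximum of one week each".

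**Concealment.** Section 6.3.2 describes the refill as "solution A or Solution B—coded by pharmacy" and states: "The investigational pharmacy at UHCMC would be the only party who knows whether the patients are receiving solution A or solution B". It also has the pump programmed, whichever solution is used, with "bupivacaine labeled at 29 mg/ml at the first visit and 30 mg/ml at the second visit". Section 2.3 names the patients and the evaluating physician as blinded. It does not name the research staff, who under 6.3.4 may obtain the data.

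**Custody.** Section 2.3 places the randomisation order at the pharmacy. Section 6.7.2 iv mentions the randomisation table and then a code kept by research staff as well as by the "UHCMC compounding pharmacy that will prepare the solutions labeled as described". Section 6.7 uses the word code for the patient identifier, which is the patient's place on that same table.

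**The concern.** A blinding code works only if the people to be blinded cannot translate it. Here the translation is printed in the protocol and does not vary by patient or visit. Sections 2.3 and 6.3.1 therefore sit badly with 6.3.2, which relies on A and B being readable by the pharmacy alone.

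The blind matters because the primary outcome is the patient's own NRS rating before and after a bolus. Expectation is also likely to be strong: under 6.2.4 the consent discussion explains the near-immediate relief that bupivacaine is thought to give. The text provides for staff contact with patients through diary reminders (6.3.2), data collection (6.3.4) and the matching of diary entries to the pump log (6.3.1). It does not say that the people doing this work are kept from the labels.

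**Working it through.** The plan gives no figure on this point and no arithmetic tests it. The check is a comparison of the sections.

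1. **Does the letter mean content, or something specific to the patient or period?** Section 6.3.1 ties A to bupivacaine and B to its absence, and has both groups receive both. A letter that meant first or second period, or that was reassigned per patient, could not satisfy both statements. The letter means content throughout the trial.

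2. **Is the letter put on the product?** Section 2.3 says that the solutions are labelled with it, in the order with bupivacaine, then without. Section 6.7.2 iv refers back to labelling already described but does not say where, so it adds nothing about what the label reveals.

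3. **What does one visible label disclose?** From steps 1 and 2, letter plus protocol gives the content for that week. Each patient receives the other solution in the other week, so it gives that week as well: 1 patient x 2 weeks = 2 patient-weeks from one label.

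4. **Would removing the printed key be enough?** No. If every patient shares the same two letters, reliably learning one patient's content decodes the letter for every other patient whose label is seen. Section 5 says that many PTM users report immediate relief when bupivacaine is present, so guesses are likely, although a guess decodes the rest only if it is correct. Section 6.3.1 also foresees programming changes after unblinding, without saying whether unblinding is per patient or at trial end. If it is per patient, the first one reveals the letters for all patients still to finish. With labels by study number and visit, disclosure of one patient's sequence reveals only that patient's 2 patient-weeks.

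5. **Does the 29 then 30 mg/ml step protect the label?** It follows the visit and not the solution, so it does not itself reveal treatment. Section 6.3.2 describes it as what the pump is programmed with. It masks the programming and does not remove a letter from the container.

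6. **Is the letter in fact visible to those who should be blinded?** The documents do not say. Section 2.3 points towards a visible letter, while the pharmacy-only statement in 6.3.2 can be read as withholding it. This is the limit of what can be concluded.

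**The case against.** The strongest reply is that 6.3.2, read literally, withholds the letter itself, and a printed key to a letter nobody sees decodes nothing. That reading is possible, and because of it the point is an inconsistency and a risk, not a failure of blinding. It does not remove the point: 2.3 says that the solutions carry the letters, and no section says how they are hidden at the refill.

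A second reply is that 6.3.2 also speaks of labelling the bupivacaine at 29 mg/ml, which could be a content-neutral product label. This is weak, because the passage concerns what is programmed into the pump. It does show that the authors took masking seriously.

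Third, the routes to bias are limited. The patients who give the ratings are blinded, nothing gives them the protocol or the label, and matching diary entries to a device log by time leaves little discretion. This stands, and it is one reason why no size of effect is claimed. Nor would relabelling stop a patient from recognising bupivacaine by its rapid effect.

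Two stronger readings are tempting. A reader might infer that the whole trial is unblinded and count 17 patients x 2 weeks = 34 patient-weeks as decoded. That only restates the trial's size and assumes that every label is seen by someone holding the protocol, which the documents do not say. A reader might also infer that research staff hold the allocation list, in conflict with 6.3.2. But 6.7 uses code for the patient identifier, and 6.7.2 iv answers a question about confidentiality of records, so that is a natural meaning there too. Custody is ambiguous, not contradictory.

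**Conclusion.** The point holds as an inconsistency between 2.3 and 6.3.1 on one side and 6.3.2 on the other, and it should be corrected. As written, A and B describe content for every patient and both weeks, so they are not a code to anyone who has the protocol.

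The consequence is conditional. If the letter is visible on the dispensed solution, one label discloses both of that patient's weeks. If it is hidden, there is no disclosure, but the protocol should then say how it is hidden. The documents support neither a shown breach nor an estimate of bias in the NRS difference. The custody wording is a secondary matter for clarification and carries little weight alone.

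**What to change.** **Labels (2.3, 6.3.1, 6.3.2).** Replace the A/B product labels with labels by study number and refill visit, for example 'Subject 07, refill 1', identical in format for both solutions. Keep the opioid name and concentration, and the visit-specific bupivacaine labelling that 6.3.2 already plans, because pump programming needs them. Describe the groups by sequence (with then without bupivacaine, or the reverse). State that the pharmacy alone holds the key.

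**Custody (6.7, 6.7.2 iv; secondary).** State that:
- the code kept by research staff is a list linking identity to study number and cannot be used to look up allocation, so the study number should no longer be the patient's place on the randomisation table;
- the pharmacy alone holds the randomisation table;
- staff who obtain or match data are blinded;
- a patient's allocation is released only after that patient's diary has been matched to the pump log, so that the unblinding foreseen in 6.3.1 after study exit remains possible.

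**Cost.** A different pharmacy label, one extra pharmacy-held list linking study number to allocation, and rewording in the sections named. Solutions, visits and sample size stay as planned. Unblinding for a patient's post-study programming would wait for that patient's diary matching, but not for the end of the trial.
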